1.2 Study design

This Phase 1 study is a randomized, participant-blind, investigator-blind, placebo-controlled safety/tolerability, pharmacokinetic (PK), and pharmacodynamic (PD) evaluation of a [REDACTED] rozanolixizumab subcutaneous (SC) dose administered to healthy participants by either a programmed syringe driver or by manual push (MP) via self-administration. As rozanolixizumab has not been administered SC to humans by MP, this study represents a preliminary assessment of the MP method prior to recommendation of this administration technique in the clinical dosing of rozanolixizumab.

Participants are divided into 2 body weight categories: ≥ 35 to < 50 kg and ≥ 50 kg. Within the higher body weight category, 16 participants were to be randomly allocated to syringe driver or MP cohorts and, subsequently, to rozanolixizumab (6 participants total) or placebo (2 participants total) (Figure 1-1). Participants of lighter body weights between ≥ 35 to < 50 kg are being investigated to a) support the newly recommended rozanolixizumab dosing with a fixed dose of [REDACTED] in adults of ≥ 35 kg to 50kg (via syringe driver administration) and (b) to assess the MP method for a [REDACTED] dose) investigational medicinal product (IMP) volume.

Within the lower body weight category, the allocation to either syringe driver or MP was to be determined by order of recruitment rather than randomization. The first 8 participants were to be allocated to the syringe driver cohort and randomly allocated to receive either rozanolixizumab [REDACTED] (6 participants total) or placebo (2 participants total). The subsequent 8 participants were to be allocated to the MP cohort and randomly allocated to receive either rozanolixizumab [REDACTED] (6 participants total) or placebo (2 participants total).

The treatment groups were planned as follows:

- Cohort 1 (participants with a body weight of ≥ 35 kg to < 50 kg) was planned to have 6 participants receive rozanolixizumab [REDACTED] and 2 participants receive placebo via syringe driver at a [REDACTED].
- Cohort 2 (participants with a body weight of ≥ 35 kg to < 50 kg) was planned to have 6 participants receive rozanolixizumab [REDACTED] and 2 participants receive placebo via MP through self-administration at a [REDACTED].
- Cohort 3 (participants with a body weight of ≥ 50 kg) was planned to have 6 participants receive rozanolixizumab [REDACTED] and 2 participants receive placebo via syringe driver at a [REDACTED].
- Cohort 4 (participants with a body weight of ≥ 50 kg) was planned to have 6 participants receive rozanolixizumab [REDACTED] and 2 participants receive placebo via MP through self-administration at a [REDACTED].

Since a [REDACTED] rozanolixizumab fixed dose has not been investigated thus far in lower weight (35 to 50kg) healthy participants, 2 sentinel study participants (1 active + 1 placebo) were to be incorporated into Cohort 1 in order to collect safety and tolerability data over a 72-hour period. The safety monitoring committee (SMC) is to convene to evaluate all available safety and tolerability data following completion of a 72-hour evaluation period and prior to staggered dosing

of remaining participants in Cohort 1. As a further precautionary step for Cohort 1, dosing of the 6 post-sentinel participants was to be staggered such that no more than 2 participants were to be dosed in a 72-hour period with a minimum of 48 hours between participants. In addition, the Rapid Alert process is in place throughout the study to ensure that exposure to the study medication is stopped if a reported event meets the stopping criteria (see protocol Appendix 8 [Section 10.8]). Cohorts are not obliged to run in numerical sequence (i.e., cohorts could run in parallel).

[figure not shown]
The eligibility of study participants is determined during a Screening Period of up to 4 weeks (Day -28 to Day -2). Once eligibility is confirmed, the study participant was to be admitted to the site (at Day -1 or the evening of Day -2) and will enter an In-Clinic Period through Day 5. Each study participant will receive a [REDACTED] SC dose of rozanolixizumab on Day 1 and may be discharged beginning at Day 5 at the discretion of the investigator. Each participant will only receive [REDACTED] IMP administration.

Beginning at Day 6, study participants will enter the Ambulatory Period and will attend the clinical site for study visits through Day 57 to allow sufficient time for systemic immunoglobulin G (IgG) levels to return to Baseline and for the assessment of anti-drug antibodies (ADAs).

The total maximum study duration per study participant is up to 12 weeks. This includes a 4-week Screening Period, 5-day In-Clinic Period, and the Ambulatory Period from Day 7 through Day 57.

Photographs of the infusion site will be taken, without participant personal or facial identification, for all participants prior to start and 30 minutes after the end of the IMP administration, and additionally upon occurrence of any injection site reaction.

Figure 1-1: Study schematic

2 STATISTICAL HYPOTHESES

Not applicable, there is no hypothesis testing in the study.

3 SAMPLE SIZE DETERMINATION

No formal statistical sample size calculation has been performed as this study constitutes a preliminary assessment of SC rozanolixizumab delivery by MP. The primary objective of the study is to evaluate the safety and tolerability of a [REDACTED] SC dose of rozanolixizumab administered to healthy participants by MP vs syringe driver. A total sample size of approximately 32 participants randomly assigned to study medication resulting in at least 6 evaluable participants per cohort is considered sufficient to meet the primary objective.

4 POPULATIONS FOR ANALYSIS

Enrolled Set: The Enrolled Set (ES) will consist of all study participants who have signed the Informed Consent Form (ICF).

Randomized Set: The Randomized Set (RS) consist of all enrolled study participants who were randomized.

Safety Analysis Set (SS): All randomized study participants who received IMP. Analysis of this set will be according to the treatment the study participants actually received and will be used for the demographic and safety analyses.

Pharmacokinetic (PK) Per Protocol Set (PK-PPS): All study participants that received active study medication and had at least 1 observable PK measurement and had no important protocol deviations affecting the PK parameters. If a study participant in the PK-PPS is missing individual time points or are otherwise unobservable, they will be included in the PK-PPS but those time points will be omitted from the PK summaries, as appropriate.

Pharmacodynamic (PD) Per Protocol Set (PD-PPS): The PD-PPS is a subset of the SS, consisting of those study participants who had no important protocol deviations affecting the PD variables, as confirmed during a pre-analysis review of the data prior to database lock.

5 STATISTICAL ANALYSES

5.1 General Considerations

This is a Phase 1 study to evaluate the safety and tolerability of a [REDACTED] SC dose of rozanolixizumab administered to healthy participants by MP vs syringe driver.

Statistical evaluation will be performed by UCB or designee with oversight by the Statistical Sciences and Innovation Department of UCB. All analyses will be performed using SAS[®] version 9.4 or later (SAS Institute, Cary, NC, USA).

Missing data will not be imputed. Outlier detection and statistical analysis of outliers will not be performed. Unless otherwise stated, Baseline will be the last non-missing data collected prior to the IMP administration ([refer Section 5.1.1.1.4](#)).

Continuous variables will be summarized by cohort and in each cohort by treatment groups rozanolixizumab [REDACTED] or placebo, and day (where applicable); with statistics including, the number of study participants, mean, standard deviation (SD), interquartile range, median, minimum, maximum, and 95% confidence interval (CI), if applicable. Categorical variables will be summarized by cohort, treatment group, and day (where applicable) with frequency counts and percentages. Coefficient of variation (CV) and geometric mean will be used for PK parameters.

In addition, the results will be summarized by administration method (manual push or syringe driver), and within administration method, by treatment group (rozanolixizumab, regardless of dose, or placebo).

When reporting relative frequencies or other percentage values, the following rules apply:

- For values where all participants fulfill certain criteria, the percentage value will be displayed as 100
- For values where the absolute frequency is zero, there will be no percentage displayed at all
- All other percentage displays will use 1 decimal place

-
- Percentages displayed based on continuous data (eg, percentage changes from Baseline) will be displayed to 1 decimal place eg, 100.0 and 0.0.
 - Unless otherwise stated, the percentages will be based on the number of participants in the respective analysis population and treatment group.

When reporting descriptive statistics, the following rules will apply in general:

- “n” will be an integer.
- Mean (arithmetic and geometric), 95% CI, SD, and median will use 1 additional decimal place compared to the original data.
- Coefficient of variance (CV [%]) will be presented with 1 decimal place.
- Minimum and maximum will have the same number of decimal places as the original value.
- If no participants have data at a given time point, then only n=0 will be presented. If n<3, only the n, minimum, and maximum will be presented. If n=3, only the n, median, minimum, and maximum will be presented. The other descriptive statistics will be left blank.

When reporting descriptive statistics for PK data, the following rules will apply with regard to rounding and precision:

- Individual values for PK concentration data will be reported to the same level of precision as received from the bioanalytical laboratory.
- Descriptive statistics for PK concentration data will be reported to the same level of precision as the individual data for the minimum and maximum, and to 1 additional significant figure for the mean (arithmetic and geometric), median, SD, and 95% CI for the geometric mean.
- Individual values for PK parameters will be reported to 3 significant figures.
- Descriptive statistics for PK parameters will be reported to 3 significant figures for minimum and maximum and to 4 significant figures for the mean (arithmetic and geometric), median, SD, and 95% CI for the geometric mean.
- Geometric CV will be reported as a percentage to 1 decimal place.
- When the mean value includes one or more replaced BLQ values then a footnote should be included to say “contains one or more BLQ value replaced by half the LLOQ value”
- A minimum of 3 values are required to calculate summary statistics. If only 2 values are available then these should be presented as the minimum and maximum with other descriptive statistics reported as missing (“-“).

Additional rules regarding handling of values that are BLQ are presented in [Section 6.1.5.2](#).

5.1.1 General study level definitions

5.1.1.1 Analysis Time Points

5.1.1.1.1 Relative day

The relative day of an event will be derived with the date of dosing as reference. Relative days for an event or measurement occurring before the date of dosing are calculated as follows:

$$\text{Relative Day} = [(\text{Event Date} - \text{Date of Dosing})]$$

The relative day for an event or measurement occurring on the date of dosing is 1 and is calculated as follows:

$$\text{Relative Day} = [(\text{Event Date} - \text{Date of Dosing}) + 1]$$

For events or measurements occurring after the date of dosing, relative day will be prefixed with '+' in the data listings and will be calculated as follows:

$$\text{Relative Day} = + [(\text{Event Date} - \text{Date of Dosing})]$$

There is no relative Day 0. Relative day is not calculated for partial dates in cases where relative day is shown in a participant data listing. In such cases, relative day should be presented as '--' in the relevant listing.

5.1.1.1.2 Study periods

The following study periods are defined:

Pre-treatment Period: This period is defined as the period prior to the date of first dose of IMP. The period ends at the day prior to the date of IMP administration.

In-Clinic Period: This period starts at the date of first dose of IMP (Day 1) and ends on the date of discharged from the clinical study center (Day 5).

Ambulatory Safety Follow-Up Period: This period starts at the day after the date of discharge (Day 5) and ends at study completion (i.e. Day 6 through Day 57).

5.1.1.1.3 Mapping of assessments performed at Early Discontinuation Visit

Participants who withdraw from the study will be encouraged to return to the clinic to complete the Withdrawal Visit.

The following rules will apply regarding the inclusion of data obtained at the early discontinuation visit in the summaries and in the data listings:

- If the early discontinuation occurs at the time of the next scheduled visit, the results will be included with all other participants' results from that visit.
- If the early discontinuation visit does not correspond to the day of a scheduled visit, the results will be mapped to the nearest scheduled visit following the last scheduled visit where assessments were performed.

-
- If the date of the early discontinuation visit is equidistant between 2 scheduled visits at which no scheduled assessments were performed, the results from the withdrawal visit will be mapped to the earliest of these visits.

The results from the early discontinuation visit will be displayed as the mapped visit and will be flagged in the data listings.

5.1.1.1.4 Definition of Baseline values

In general, Baseline will be the last non-missing value prior to dosing. Scheduled or unscheduled measurements can be used as the Baseline value.

5.1.1.2 Protocol Deviations

Important protocol deviations are deviations from the protocol which potentially could have a meaningful impact on study conduct, or on the PK, PD and key safety for an individual study participant. The criteria for identifying important protocol deviations will be defined within the appropriate protocol-specific document. Important protocol deviations will be reviewed as part of the data cleaning process and all important deviations will be identified and documented before unblinding to confirm exclusion from analysis sets.

After all data have been verified/coded/entered into the database, a blinded data review will be performed prior to database lock, at a Data Evaluation Meeting (DEM). The purpose of this review meeting will be to examine all protocol deviations, define the PK-PPS and PD-PPS, and to verify the quality of the data. The data evaluation will also help in guiding decisions on how to manage data issues on a case by case basis (e.g., missing values, dropouts, and protocol deviations). Protocol deviations (e.g., missing assessments or visits) related to coronavirus disease-19 (COVID-19) will be listed separately and will be reviewed for the definition of the PK-PPS and PD-PPS analysis sets.

All Important Protocol Deviations (IPDs) will be discussed and documented at the DEM together with any decisions regarding exclusion from analysis sets. If necessary, appropriate actions will be implemented in the SAP amendment before locking the database. After the DEM, resolution of all issues, and documentation of all decisions, the database will be locked.

5.1.1.3 Treatment assignment and treatment groups

Treatment assignment for the SS, PK-PPS and PD-PPS will be according to the actual treatment received. Listings and summaries will be presented by cohort and treatment group.

The following label conventions and order will be used in the TFLs (except for PK analysis)

- Cohort 1 - ≥ 35 kg to < 50 kg, Syringe driver
 - Placebo via Syringe Driver
 - Rozanolixizumab [REDACTED] Syringe Driver
- Cohort 2 - ≥ 35 kg to < 50 kg, MP

-
- Placebo via MP
 - Rozanolixizumab [REDACTED] MP
 - Cohort 3 ≥ 50 kg, Syringe driver
 - Placebo via Syringe Driver
 - Rozanolixizumab [REDACTED] Syringe Driver
 - Cohort 4 ≥ 50 kg, MP
 - Placebo via MP
 - Rozanolixizumab [REDACTED] MP
 - Syringe Driver, All Participants
 - Placebo
 - Rozanolixizumab
 - MP, All Participants
 - Placebo
 - Rozanolixizumab

The following label conventions and order will be used in the PK TFLs:

- Rozanolixizumab via Syringe Driver, All
- Rozanolixizumab via MP, All

The explanatory description of each cohort may be dropped from the labels if space is limited. For listings, the cohort description and the treatment name will be written out in full.

5.1.1.4 Center pooling strategy

Not applicable, this is a single center study.

5.1.1.5 Coding dictionaries

Adverse events and medical history will be coded using Version 23.1 of the Medical Dictionary for Regulatory Activities (MedDRA[®]). Medications will be coded according to the World Health Organization Drug Dictionary (WHODD). Medical procedures will not be coded.

5.1.1.6 Multicenter studies

This is a single center trial, therefore this section is not applicable.

5.2 Participant Disposition

The number of participants who were enrolled, randomized into the study, included in each analysis set, and completed or prematurely discontinued from the study, as well as the reason for discontinuation, will be summarized by cohort and treatment group.

Screen failure reasons will be summarized based on the ES.

In addition, the following listings will be presented by cohort and treatment group:

- Participant disposition (ES)
- Participant analysis sets (ES)
- Participant discontinuing from the study (RS)
- Study visit dates (RS)

The listing of participants disposition will include the date of informed consent, date of randomization, date and time of dosing, date of premature study termination, primary reason for premature discontinuation (if applicable), date of final contact, and date of premature unblinding and reason for code break (if applicable).

The listing of study discontinuation will include the reason for discontinuation and the number of days since dosing.

The number and percentage of study participants who discontinued due to adverse events (AEs) will be summarized separately by cohort and treatment group, based on the randomized participants. This will be used for European Union Drug Regulating Authorities Clinical Trials (EudraCT) reporting.

5.3 Primary Endpoint(s) Analysis

The primary endpoint is:

- Incidence of Treatment-emergent adverse event (TEAE).

5.3.1 Definition of endpoint(s)

A TEAE is defined as any AE with a start date/time on or after first dose of study medication until 8 weeks after dosing of study medication (termination or withdrawal visit) .

5.3.2 Main analytical approach

All AEs and serious adverse events (SAEs) will be collected from the signing of the ICF until the Safety Follow-up/Withdrawal Visit. All AEs will be coded ([Section 5.1.1.5](#)) and categorized by intensity (mild/moderate/severe) and relationship to study drug (related/not related). Only TEAEs will be included in the summary tables and listings.

The number and percentage of participants who experience TEAEs will be summarized by cohort, treatment group, system organ class (SOC) and preferred term (PT) based on the safety analysis set. Summaries of TEAEs will include the following:

- Overview of TEAEs (overview including number and percentage of participants with any TEAEs, serious TEAEs, discontinuations due to TEAEs, drug-related TEAEs, severe TEAEs, TEAEs of special interest and TEAEs leading to death; event counts will also be included)
- Incidence of TEAEs
- Incidence of TEAEs leading to study medication interruption
- Incidence of serious TEAEs
- Incidence of non-serious TEAEs
- Incidence of TEAEs by relationship to study medication
- Incidence of TEAEs by maximum relationship to study medication
- Incidence of TEAEs by intensity
- Incidence of TEAEs by maximum intensity
- Incidence of non-serious TEAEs by relationship
- Incidence of serious TEAEs by relationship
- Incidence TEAEs of special interest
- Incidence of TEAEs of Focus (see Appendix 6.1.8)
- Incidence of TEAEs of special monitoring
- Incidence of TEAEs by TE ADA status

In case of missing or incomplete dates, AEs will be assumed to be treatment-emergent and will be handled as described in [Section 6.1.5.3](#).

Summary tables will contain counts of participants, percentages of participants (in parentheses), and the number of events where applicable. A participant who has multiple events in the same SOC and PT will be counted only once in the participant counts but all events will be included.

In summaries including relationship, the following relationships will be summarized: 'not related', 'related'. Participants who experience the same event multiple times will be included in the most related category for tabulations by maximum relationship. Events with missing relationship will be considered as 'related' but recorded as missing in the listings.

Adverse event summaries will be ordered alphabetically by SOC and decreasing frequency of PT within SOC in the "Rozanolixizumab" cohort 1 column for tables including event counts. For tables including only number and percentage of participants, summaries will be ordered alphabetically by SOC and decreasing incidence of PT within SOC in the "Rozanolixizumab" column.

A listing will be presented by treatment group for all AEs and will include the onset date/time and outcome date/time of the event (including relative days), the AE duration (derived), pattern of event, intensity, relationship, action taken and outcome. In addition, the listing will flag AEs that led to discontinuation, TEAEs, and SAEs.

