- r Applicable only to participants experiencing severe and/or serious headache(s). The Headache Questionnaire will be performed daily until resolution (ie, if headache becomes moderate or mild, normal collection of AEs should apply). Headache Questionnaire should be assessed after Day 5 (at the investigator's discretion) if participants are kept longer in the unit for severe headache.
- s A neurological assessment is to be performed by the investigator or designee for those participants who experience severe and/or serious headaches with a frequency as clinically indicated. This assessment will include:
- 1) General appearance, including posture, motor activity, vital signs, and meningeal signs, if indicated;
  - 2) Cranial nerves;
  - 3) Motor system, including muscle tone and power and sensory system – light touch;
  - 4) Reflexes, including deep tendon reflexes;
  - 5) Coordination, gait (if possible);
  - 6) Fundoscopy.
- The neurological assessment may be performed after Day 5 (to the investigator's discretion) if headache continues. The neurological assessment may be repeated if headache continues and it is clinically indicated and at the discretion of the investigator. In study participants who report severe headache, other diagnostic procedures including a CT scan (if indicated, and at the discretion of the investigator) and lumbar puncture for CSF collection (if clinically indicated, and at the discretion of the investigator) should be performed (see Section 8.3.7.1.3 and Section 8.3.7.1.4, respectively).
- t Complement and cytokine sampling taken predose for all participants and at 4 and 8 hours post event only if an infusion reaction or AE of special monitoring is observed. Backup samples could be stored for later biomarker analyses (up to 20 years).
- u Anti-rozanolixizumab antibodies will be assessed predose and on Days 10, 16, 22, and 57.

In addition to those detailed in [Table 1-1](#), the assessments in [Table 1-2](#) may be required in case of infusion reactions or adverse events (AEs) of special monitoring (severe headache, severe gastrointestinal disorders [eg, diarrhea, abdominal pain, vomiting]). Note that additional vital sign measurements may be taken based on the timing of the assessments.

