5.5.1 Immunogenicity Analyses

The development of antidrug antibodies during the study will be evaluated to assess the immunogenicity potential of the study drug.

The anti-drug (rozanolixizumab) antibody (ADA) screening status (positive or negative screen), confirmatory status (positive or negative immunodepletion), and the titer for “positive immunodepletion” samples at each scheduled assessment during the In-Clinic and SFU Periods will be presented.

The results of the ADA analyses will be listed and summarized by cohort treatment group (refer [section 5.1.1.3](#)) and time point for the SS.

Anti-drug antibodies will be measured using a three-tiered assay approach: screening assay, confirmatory assay and titration assay. All immunological analyses will be exploratory.

Samples will first be evaluated in the screening assay using a false positivity rate of 5% (reported as ‘negative screen’ or ‘positive screen’), followed by analysis of screened positive samples in the confirmatory assay (which is a drug depletion assay) to confirm the true positivity of the samples (reported as ‘negative immunodepletion’ or ‘positive immunodepletion’). Samples that are confirmed as positive will be evaluated in a titration assay to quantify the ADA level and will be reported as titer (reciprocal dilution factor including minimum required dilution (MRD)).

The ADA status should be determined for each visit where samples were taken for ADA analysis.

- Sample values that are either ‘negative screen’ or ‘positive screen’ and ‘negative immune depletion’ will be defined as ADA negative.
- Sample values that are ‘positive screen’ and ‘positive immune depletion’ will be defined as ADA positive.

In addition, the anti-drug antibody status will be further classified based on participant levels as outlined below. This classification should be done for entire study duration (i.e. the treatment period including SFU sampling time point).

1. **Pre ADA negative – treatment induced ADA negative:** Includes participants who are negative at Baseline and antibody negative at all sampling points post treatment. This group also includes participants who have a missing pretreatment sample (either missing or insufficient volume) at Baseline with all ADA post-treatment samples negative.

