2. **Pre ADA negative – treatment induced ADA positive:** Includes participants who are negative at Baseline and antibody positive at any sampling point post treatment. This group also includes participants who have a missing pretreatment sample (either missing or insufficient volume) at Baseline with one or more ADA positive post-treatment samples.
3. **Pre ADA positive – treatment reduced ADA:** Includes participants who are positive at Baseline, and antibody negative at all sampling points post treatment.
4. **Pre ADA positive – treatment unaffected ADA:** Includes participants who are positive at Baseline and are positive at any sampling point post treatment with titer values of the same magnitude as Baseline (ie, less than a predefined fold difference increase from the Baseline value, i.e. the minimum significant ratio (MSR) determined during assay validation).
5. **Pre ADA positive – treatment boosted ADA positive:** Includes participants who are positive at Baseline and are positive at any sampling point post treatment with increased titer values compared to Baseline (greater than a predefined fold difference increase from Baseline value, i.e. the MSR determined during assay validation).
6. **Inconclusive:** Includes participants who have a positive or negative pretreatment sample and at least one post-treatment samples are missing, while other post-treatment samples are ADA negative.

Based on the overall ADA participant classification above, the following will be determined and presented in tables:

- Total prevalence of pre-Antibody: n/N % number of participants that are pre ADA positive, i.e. from categories 3, 4, 5.
- Total incidence of treatment-emergent ADA positive: n/N % number of participants in category 2 and category 5.

The following summaries, figures and listings will be produced and will be presented:

-
- Summary table displaying the number and percentage of participants with a positive ADA status and negative ADA at the time of each visit by cohort and treatment group.
 - Summary tables displaying the number and percentage of participant in each of the ADA participant categories (1 – 6), total prevalence of pre-Antibody and total incidence of treatment-emergent ADA positivity as defined above by cohort treatment group.

Spaghetti plots of ADA titer (y-axis) by visit (x-axis). This plot will include the following ADA participant categories:

- a) Category 2: Pre ADA negative – treatment-induced ADA positive

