5.8 Subgroup analyses

Not applicable, no subgroup analyses are planned for this study

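### The table of TEAEs by TE ADA status has no denominator of its own, so the SAP default can hide or reverse a difference between ADA groups; separately, it counts TEAEs that began before any positive postdose sample

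*SAP*

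**What the plan says.** SAP 5.3.2 ends its list of TEAE summaries with "Incidence of TEAEs by TE ADA status". It gives no levels of status, no denominator and no rule on onset. The same section says that TEAE counts and percentages "will be summarized by cohort, treatment group, system organ class (SOC) and preferred term (PT) based on the safety analysis set".

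SAP 5.1 supplies the general rule: "Unless otherwise stated, the percentages will be based on the number of participants in the respective analysis population and treatment group". Nothing overrides it for this table. SAP 5.8 defines no subgroup denominators either: "Not applicable, no subgroup analyses are planned for this study".

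On timing, SAP 5.3.1 states: "A TEAE is defined as any AE with a start date/time on or after first dose of study medication until 8 weeks after dosing". Footnote u of Protocol Table 1-1 states: "Anti-rozanolixizumab antibodies will be assessed predose and on Days 10, 16, 22, and 57". SAP 5.5.1 sorts each participant into one of six ADA categories and adds: "This classification should be done for entire study duration". It defines the treatment-emergent group as follows: "Total incidence of treatment-emergent ADA positive: n/N % number of participants in category 2 and category 5". It does not say how categories 1, 3, 4 and 6 (Inconclusive) enter the TEAE table.

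**The concern.** The default denominator suits most tables in the SAP 5.3.2 list. Intensity, relationship and seriousness are properties of the event, so every participant in the treatment group is at risk of contributing to each row. TE ADA status is a property of the participant. Dividing both status groups by the same treatment-group total splits the overall TEAE percentage into parts. It does not give the risk in each group.

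This is the only summary in the SAP that relates antibodies to adverse events. Read as written, it could show a lower figure for TE ADA-positive participants when their observed risk is higher.

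The timing issue is distinct and would remain after the denominator is corrected. A TEAE on the day of infusion, in a participant whose first positive postdose sample comes weeks later, is tabulated under TE ADA-positive.

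**Working it through.** The documents give no figure for this table, so there is nothing to reproduce. The check is direct arithmetic.

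**Inputs**
- Active participants: 6 per cohort, hence 12 per administration method and 24 in all (Protocol 7.2; SAP 5.1.1.3 for the by-method columns).
- Illustrative TEAE risk: 38 participants, 77.6%, on rozanolixizumab in the earlier healthy-participant study UP0060 (Protocol 2.2). This implies 38/0.776 ≈ 49 participants.
- Number TE ADA-positive, k: not in the documents, so it is varied as an assumption. For simplicity the rest are taken as TE ADA-negative, with none Inconclusive.

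**Denominator.** Let N be the treatment-group size, with TEAEs in a of k positive and b of N − k negative participants. Under the default:
- displayed positive = a/N = (k/N) × (a/k)
- displayed negative = b/N = ((N − k)/N) × (b/(N − k))
- displayed ratio = [k/(N − k)] × true risk ratio.

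Whole-participant examples:

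| N | k | TEAEs, positive vs negative | Default display | Within status |
|---|---|---|---|---|
| 6 | 2 | 2/2 vs 4/4 | 33.3% vs 66.7% | 100% vs 100% |
| 6 | 2 | 2/2 vs 3/4 | 33.3% vs 50.0% | 100% vs 75.0% |
| 12 | 3 | 3/3 vs 6/9 | 25.0% vs 50.0% | 100% vs 66.7% |

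The first row shows a difference where there is none. The other two reverse the order.

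Expected display when the true risk is 38/49 in both groups:

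| N | k | Positive | Negative | Displayed ratio (truth 1) |
|---|---|---|---|---|
| 6 | 1 | 12.9% | 64.6% | 0.20 |
| 6 | 2 | 25.9% | 51.7% | 0.50 |
| 12 | 3 | 19.4% | 58.2% | 0.33 |
| 6 | 3 | 38.8% | 38.8% | 1.00 |
| 6 | 5 | 64.6% | 12.9% | 5.0 |

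The positive percentage cannot exceed k/N, which is 16.7% for 1 of 6. The two columns look equal only when the true risk ratio is (N − k)/k: 5.0 for 1 of 6, 2.0 for 2 of 6, 3.0 for 3 of 12. The figure still moves with risk. At N = 12 and k = 3, having 0, 1 or 3 positive participants with a TEAE gives 0%, 8.3% or 25.0%.

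**Timing.** The TEAE window opens at dosing on Day 1, and the first postdose ADA sample is on Day 10. Days 1 to 9 are 9/57 = 15.8% of the 57-day period. That is a share of time, not of events, because the documents give no onset distribution. The largest gap between samples is Day 22 to Day 57, which is 35 days. If the first positive sample is Day 57, the antibody could have appeared at any point in that gap.

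**The case against.** The strongest reply is that the SAP is silent on this table and does not prescribe a wrong one. It gives a title only, and a table by participant status is naturally laid out with status-specific totals. Table shells, which the SAP cites for the AEs of focus and which are not in the documents, might do exactly that. This stands in part: the whole-group denominator follows from a general default, not from an instruction for this table. But the default is explicit and applies unless something overrides it, and nothing does. Shells with status-specific totals would depart from the SAP as written.

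Next, within-status risk can be recovered. SAP 5.3.2 requires participant counts as well as percentages, and SAP 5.5.1 tabulates the number in each ADA category by cohort and treatment group. AE onset and ADA results are also listed by participant. This is true and limits the harm, but the printed percentages would still mislead anyone who does not redo the division.

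On timing, category 5 participants are already ADA-positive at Baseline, and in category 2 the first positive sample is not the moment the antibody appeared. A reader might infer that these TEAEs occurred before any antibody existed. The documents do not support that. They show only that no positive postdose sample had yet been taken.

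**Conclusion.** The point holds as a gap in specification with a misleading literal result. Under the SAP default, each percentage mixes the share of participants in an ADA status with the risk within that status. Depending on the share, this can hide, create or reverse a difference. The size depends on the TE ADA-positive share, which is assumed throughout. With half the group positive there is no distortion; with 1 of 6 positive, equal risks appear as a fivefold difference.

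A reader might infer that the percentages reflect how common antibodies are and carry no information on risk. That goes too far: they are a product of the two, and only when the within-status risks are equal does the share alone drive the contrast. The share in question is also the incidence of treatment-emergent ADA, since the SAP keeps the word prevalence for antibody present before dosing.

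The timing problem is real, but its size in events cannot be stated from the documents.

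The consequence is limited. SAP 2 plans no hypothesis testing, SAP 5.5.1 calls the immunological analyses exploratory, there are 6 active participants per cohort, and the primary endpoint of overall TEAE incidence is untouched. The change should be made, but the study does not depend on it.

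**What to change.** Add to SAP 5.3.2, for this table only:

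- The denominator is the number of participants in each TE ADA status level within the treatment group, and results are shown as n/N with the percentage.
- The levels are TE ADA-positive (categories 2 and 5), TE ADA-negative (categories 1, 3 and 4) and Inconclusive (category 6), each shown separately.
- For category 2 and 5 participants, a listing flags each TEAE's onset relative to two dates: the last sample before the first TE ADA-positive sample, and that positive sample itself. Onset between the two is marked indeterminate, for example between Days 22 and 57 when Day 57 is the first positive.

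A simple split into before and after the first positive sample is not advised. With the 35-day gap, someone who became positive on Day 23 would have every event from Day 23 to Day 56 labelled as before the antibody.

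The cost is a few sentences, status-specific totals in one table and a flag in one listing. The dates needed are already collected. The drawback is small denominators, often one to three participants, which is why n/N should always be visible.
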